10.0 Risks to Subjects and Mitigation Strategies

- Small risk of loss of confidentiality, but every effort will be made to prevent this and keep participant information confidential. If the participant/LAR wish provides an email address and/or phone number, the study team may communicate with them and they will be informed that this is not a secure method and could be accessed by someone else in the event of a security breach. The hospital is not liable for security breaches.
- Minimal discomfort or bruising may occur with drawing blood and IV placement. The participant may be given the option of a numbing agent to help ease the pain of needle sticks.
- When answering the brief questionnaires, the questions asked may be uncomfortable or embarrassing. These risks are minimum and unlikely to occur. The participant does not have to give any information they do not want to give. Confidentiality will be protected to the greatest extent possible and answers will not be released to the care team.

SHORT TITLE: Naltrexone Neuroimaging

- Side effects to naltrexone occur in ~10% of patients, are typically mild and go away on their own (e.g., nausea) and do not differ from those receiving a placebo (e.g., sugar pill). Allergic reaction to naltrexone is rare and usually happens right away after taking the medicine. Symptoms include hives and difficulty breathing. Medications for immediate treatment of severe allergic reactions and trained personnel will be available in the clinic where the study drug is given.
- Genetic testing carries the possibility of discrimination. However, a Federal law called the Genetic Information Nondiscrimination Act (GINA) generally makes it illegal for health insurance companies, group health plans, and most employers to discriminate based on genetic information. Additionally, results will be kept in the study record and not released to your medical record.
- Incidental finding from the neuroimaging (e.g., fMRI) may occur. Whenever brain imaging is done, there is a chance of finding something unexpected and unrelated to the research study that may have some clinical implications. The neuroimaging used in this study is for research purposes only and is not the same as clinical neuroimaging.

11.0 Potential Benefits

Participants have the possibility of direct benefit should they experience eating disorder symptom reduction after taking naltrexone (e.g. reduced urge to binge and/or purge or lack of positive reinforcement from binge/purge). It is plausible to experience an effect after a one-time dose based on evidence of complete opioid antagonism as soon as 2 hours after a one-time dose(13, 14). Should individuals experience a benefit, they may choose to share this information with their treating clinician and consider initiating ongoing therapy with naltrexone. Sharing such information with the treating clinician is outside the scope of this study and would solely be at the discretion of the participant.

The knowledge gained from this study has the potential to further our understanding of alterations in the reward pathway and their contribution to eating disorder and benefit society through advancement of mental health knowledge and treatment.

12.0 Investigator Assessment of Risk/Benefits Ratio:

Select as applicable:	Pediatric Risk Category:	
	Category 1	Research not involving greater than minimal risk (45 CFR §46.404 and 21 CFR §50.51)
	Category 2	Research involving greater than minimal risk but presenting the prospect of direct benefit to the individual subjects. (45 CFR §46.405 and 21 CFR §50.52)
	Category 3	Research involving greater than minimal risk and no prospect of direct benefit to individual subjects, but likely to yield generalizable knowledge about the subject's disorder or condition. (45 CFR §46.406 and 21 CFR §50.53)
	Category 4	Research not otherwise approvable which presents an opportunity to understand, prevent, or alleviate a serious problem affecting the health or welfare of children. (45 CFR §46.407 and 21 CFR §50.54)
Select if applicable:	Adult Risk Category:	
	Not Greater than Minimal Risk	
	Greater than Minimal Risk	

13.0 Payment, Reimbursement and Tangible Property provided to subjects

Payment to Subjects: Greenphire or CM approved equivalent will be used to provide payment of \$400 to each participant at the conclusion of the study day as renumeration for their time.

Tangible Property: N/A

14.0 Compensation for Research-Related Injury

No compensation for research-related injury will occur. Should a serious adverse event occur during the study day, the participant will be taken to the nearest emergency department or the emergency department of their choice (e.g., Children's Mercy or KUMED).

15.0 Economic Burden to Subjects

Participants will not be responsible for the cost of any study procedure.

16.0 Permission/Accent/Consent Process and HIPAA authorization

Full written permission and assent and HIPAA authorization will be obtained for pediatric participants and consent for adult/emancipated participants. The study will be explained, and participants/LAR will be given as much time as they need to review PAC, ask questions and come to a decision. This may occur over the phone, virtually (e.g., CM approved platform like Teams) or in person based on participant preference and available resources to the study team. PAC will be signed by hand or electronically.

The study is requesting the option of using a telephone/telemedicine consent process for initial consenting. CM telephone/telemedicine consent process research policy will be followed.

A waiver of written documentation of consent and alteration of HIPAA authorization (p/a/c form provided but signature will NOT be obtained, e.g. verbal consent) is requested for participants who will re-consent at age 18 per CMRI policy. Patients who were <18 at initial enrollment, but turn 18 after study procedure completion will have signed parental consent/participant assent (confirmed by study staff) and completed all study procedures, but may have PHI stored in the study DCF while the study remains open which represents no more than minimal risk to the participant (and involves no procedures for which written consent is normally required outside of the research context). PHI will not be reused or disclosed to anyone not involved in this research. The research cannot practicably be conducted without the Alteration of HIPAA authorization as many of the patients who turn 18 after study procedure completion may already be treated and discharged. Data from all these participants is needed to describe aims of the study. These participants will be identified by review of study participant DCFs. If verbal re-consent cannot be accomplished via telephone/telemedicine, de-identification of study samples and data will occur.

A partial waiver of HIPAA authorization is requested for pre-screening/recruitment. A report will be generated from HIM that includes PHI of potential participants (e.g., name, MR, diagnosis code). Use of PHI is no more than minimal risk to the privacy of the individuals because PHI will be kept on CM protected network, accessed by study team and destroyed with other study documents. This will allow for the description of recruitment efforts in aggregate form (e.g., number of patients enrolled/number of patients eligible). This PHI will not be reused or disclosed to anyone or entity outside of the study team. Without this waiver, recruitment would not be feasible as we would fail to identify potential study participants. Relying solely on provider or patient self-referral for study participation would compromise the ability to complete the study given the relatively small patient pool of which to recruit from. In addition, these individuals may be screened for inclusion/exclusion criteria to avoid unnecessary

SHORT TITLE: Naltrexone Neuroimaging

contact if patient does not meet criteria. This approach has been successful in recruiting for an IRB-approved study in adolescents with eating disorders.

17.0 Identifiable Information

1. Name/Initials	 Accessed only	 Recorded
2. All elements of date (except year) directly related to an individual (e.g. date of birth, admission date, discharge date, date of death)	 Accessed only	 Recorded
3. Medical record number	 Accessed only	 Recorded
4. Account number	 Accessed only	 Recorded
5. Health plan identification number	 Accessed only	 Recorded
6. Social Security Number	 Accessed only	 Recorded (only if needed, see above)
7. Device identifiers and serial number	 Accessed only	 Recorded
8. Certificate/License number	 Accessed only	 Recorded
9. Telephone number	 Accessed only	 Recorded
10. Fax number	 Accessed only	 Recorded
11. Email addresses	 Accessed only	 Recorded
12. Web addresses (URLs); Internet IP addresses	 Accessed only	 Recorded
13. Street address, city, county, precinct, zip code or equivalent geographical codes	 Accessed only	 Recorded
14. Full face photographic images and any comparable images	 Accessed only	 Recorded
15. Biometric identifiers, including finger and voice print	 Accessed only	 Recorded
16. Vehicle identifiers and serial numbers, including license plate number	 Accessed only	 Recorded
17. Any other unique identifying number, characteristic or code that may help identify individual participants including their initials (e.g. student or employee ID number)	 Accessed only	 Recorded
18. Elements of date, including year, for persons 90 years or older	 Accessed only	 Recorded
19. Other:	 Accessed only	 Recorded

18.0 Genetic Analysis Information

Single nucleotide polymorphism (SNPs) analysis and genomic sequencing may occur as part of this study for research purposes only to explore the impact of genetic variation on pharmacokinetics, pharmacodynamics and/or disease. Genetic information may be stored in the Adolescent Medicine Pharmacogenomic Repository (AMP) (IRB#13020033).

19.0 Sharing of Results with Subjects

Results (including genetic analysis or any incidental findings on neuroimaging) will not be shared individually with participants. It is the intent of study to publish study results and thus participants may learn about study results in such publications.

20.0 Storage/Banking of Data and Specimens for Future Research

Data and leftover specimens will be stored in the existing Adolescent Medicine Pharmacogenomic Repository (AMP), IRB#13020033 which describes the potential for sharing of deidentified samples with other researchers per IRB protocol.

21.0 Withdrawal of Subjects

Participants may withdrawal at any time during the study. To withdrawal participants will notify the study team in writing that they wish to withdrawal. Study procedures will cease. Any data collected will be retained for potential analysis.

22.0 Data Analysis:

Outcome analyses. Outcomes are defined per Table 2. SA1. *Response*. fMRI data will be analyzed in AFNI in two ways: 1) region of interest (ROI) analysis in *a priori* reward ROIs including the ventromedial prefrontal cortex, ACC and striatum and 2) exploratory whole brain analysis to identify regions outside the reward network that may also respond to naltrexone (e.g., insula, dorsolateral prefrontal cortex, dorsal ACC). We have chosen to use a pre-defined ROI analysis which will be selected from a meta-analysis of passive viewing food tasks and MID studies using neurosynth.org or similar(29). Although ROI approaches do present challenges in fMRI analyses, this hypothesis-driven approach has been chosen to focus the primary analysis to test targeted reward related changes associated with treatment. Exploratory analysis described below will use advanced fMRI analysis approaches to take advantage of the richness of the whole-brain data. SA2. *Optimal paradigm*. The %BOLD changes will be compared between paradigms by LMM using paradigm (PFV, MID) and time (pre, post) as fixed-effects, and random individual and/or paradigm intercepts. SA3. The changes in %BOLD and changes in *Exposure* (log-scale) will be correlated by Pearson's correlation coefficient; the 95% CI will be estimated by non-parametric bootstrap using the bias-corrected and accelerated method.

PKPD analysis. Kinetica 5.0 or similar software will be used to model PK parameters (e.g., C_{max} , AUC_{0-inf}).

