2.0 Objectives

The overall goal of this project is to generate pilot data to support the development of fMRI as a pharmacodynamic biomarker of opioid antagonism in adolescents with ED, which will be accomplished through the following specific aims (SA):

SA1. Define the extent of within individual reward system modulation and identify the brain region most responsive to opioid antagonism in adolescents with binge/purge ED. We will use fMRI to detect percent blood oxygenation level dependent (%BOLD) changes pre- and post-opioid antagonist treatment (i.e., naltrexone) within individuals during a food reward and general reward-related task using regions of interest (ROI) analysis. We hypothesize that the anterior cingulate cortex (ACC) will be most responsive to naltrexone in adolescents with ED during food reward.

SA2. Determine the fMRI reward paradigm most sensitive to opioid antagonism in adolescents with binge/purge ED. Using the method described in SA1, we anticipate that the food paradigm will be more sensitive (e.g., higher t-score) in reward ROI to opioid antagonism in our target population.

SA3. Describe the naltrexone exposure-brain response relationship using fMRI in adolescents with binge/purge ED. We will link pharmacokinetic (PK) parameters of exposure with %BOLD change in subjects during the reward paradigms using ROI analysis. Based on our preliminary data suggesting

SHORT TITLE: Naltrexone Neuroimaging

widely variable maximum plasma concentrations (C_{max}) of naltrexone in adolescents with ED (17-fold), we hypothesize that reduced C_{max} will be associated with reduced activation in reward-related ROIs.

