4.0 Study Endpoints

Outcomes	Exploratory Outcomes

Primary:
 
• RESPONSE (SA1) - defined by $\Delta\%BOLD$ pre/post-ntx in ROI 
Secondary:
 
▪ ROI (SA1) - defined by coordinates with largest response▪ OPTIMAL PARADIGM (SA2) – paradigm (PFV or MID) resulting in larger response▪ EXPOSURE (SA3) – defined by ntx C_{max}	
▪ RESPONSE x OPRM1 genetic variation▪ RESPONSE x metabolomic profile▪ RESPONSE x impulsivity▪ RESPONSE x negative urgency▪ RESPONSE x delayed discounting▪ EXPOSURE x AKR1C4 genetic variation▪ EXPOSURE x metabolomic profile

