Assessments (including categories of data collected). Self-report data will be captured via electronic surveys (e.g., Research Electronic Data Capture -REDCap), structured interview, study records. Anthropometrics. Height, blind weight will be obtained; body mass index (BMI), BMI z-score, % ideal body weight will be calculated. Structured interview. Study staff will obtain participant demographics, ED, medical, family & menstrual history. Confidential social history will be obtained via self-report electronic survey. Laboratory. Urine drug panel will objectively assess illicit substance use (e.g., nicotine, THC) at baseline along with urine pH and specific gravity and used as covariates in analysis. Eating Disorder Symptom Burden. The EPSI will evaluate symptom burden at baseline. The EPSI has excellent validity and reliability derived from a diverse population, has published normative data(8, 9) and includes various sub-scales (e.g., body dissatisfaction, cognitive restraint) that will allow characterization of our sample. Hunger. Before each scan, hunger will be assessed. Safety. Baseline heart rate and blood pressure will be recorded. Physical symptoms that may occur after naltrexone administration will be assessed.

Reward System Modulation by fMRI. Each participant will undergo two fMRI scans on the same day. Scan #1 (pre) will be in the fed state *before* naltrexone administration. Scan #2 (post) will be in the fed state 2 hours *after* naltrexone. Each scan will last approximately 1 hour and involve two reward activation paradigms(10-12): passive food view (PFV) and monetary incentive delay (MID). These two reward activation paradigms provide distinct insight and will generate pilot data to support the choice of the optimal paradigm for further testing of reward system modulation in adolescents with eating disorders. PFV provides a paradigm that is relevant to the target behaviors (i.e., binge eating, purging), has been evaluated in ED patients, in response to naltrexone in adults, and is expected to activate food cue-reactivity regions (e.g., prefrontal cortex). MID is a widely used paradigm in adolescents to detect reward anticipation and receipt particularly in the striatum and is currently being used to study the developmental trajectory of reward processing in the longitudinal Adolescent Brain Cognitive Development (ABCD) trial. To the greatest extent possible, we will harmonize our fMRI parameters with those published for ABCD.

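### SA2 is to compare pre-to-post %BOLD changes between PFV and MID, but the mixed model as listed has no paradigm × time term, and no test or interval for that difference is specified

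*Combined protocol and SAP*

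**What the plan says.** Section 4.0 (Study Endpoints) defines response as the pre/post-naltrexone change in %BOLD in the ROI, and the secondary SA2 outcome as the "paradigm (PFV or MID) resulting in larger response". Section 2.0 gives the hypothesis: "we anticipate that the food paradigm will be more sensitive (e.g., higher t-score) in reward ROI to opioid antagonism". It also says SA2 uses the SA1 method, which measures %BOLD "changes pre- and post-opioid antagonist treatment (i.e., naltrexone) within individuals during a food reward and general reward-related task".

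The only description of the SA2 analysis is in Section 22.0: "The %BOLD changes will be compared between paradigms by LMM using paradigm (PFV, MID) and time (pre, post) as fixed-effects". The sentence ends by listing random intercepts for individual and/or paradigm. No section names a paradigm × time interaction, an equivalent contrast, or the coefficient on which SA2 will be judged. The same section names the "reward ROIs including the ventromedial prefrontal cortex, ACC and striatum" for the ROI analysis.

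**The concern.** The SA2 sentence states the right aim in words and then lists a model whose terms do not deliver it. Main effects of paradigm and time describe an average level difference between tasks and an average change over tasks. Random intercepts shift levels only. None of these is the difference between the PFV change and the MID change.

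Section 9.0 says that the two paradigms "will generate pilot data to support the choice of the optimal paradigm for further testing of reward system modulation". An analyst who fitted the listed terms and read the paradigm coefficient as the SA2 result would be choosing a task on a mixture of its baseline level and its drug response. Section 9.0 describes the tasks as engaging different regions: PFV "is expected to activate food cue-reactivity regions (e.g., prefrontal cortex"), while MID is used "to detect reward anticipation and receipt particularly in the striatum". A level gap within a given ROI is therefore plausible, although the documents give no size for one.

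**Working it through.** **Inputs.** The outcome definition is in Section 4.0, the model terms in Section 22.0, and enrolment of up to 50 in Section 5.0. The plan states no alpha, power, SD or effect size for SA2, so there is no planned figure to reproduce. Every SD and effect size below is an assumption.

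**Cell means.** Let G be the pre-dose PFV level minus the pre-dose MID level, dP and dM the two pre-to-post changes, and D = dP - dM.

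| | Pre | Post |
|---|---|---|
| PFV | m + G | m + G + dP |
| MID | m | m + dM |

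SA2 asks about D.

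**Model as listed**, fitted mean = b0 + bP·paradigm + bT·time:

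- Fitted difference in change: (b0 + bP + bT) - (b0 + bP) - (b0 + bT) + b0 = 0, whatever the data.
- With complete data, bT = (dP + dM)/2, the average change.
- With complete data, bP = mean PFV - mean MID = G + (dP - dM)/2 = G + D/2.

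So bP is zero when G = -D/2. It has the opposite sign to D when G is opposite in sign to D and larger than |D|/2.

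**Example (assumed dP = -0.30, dM = 0, so D = -0.30).**

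| G | bP = G - 0.15 |
|---|---|
| 0 | -0.15 |
| 0.15 | 0 |
| 0.30 | +0.15 |

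The drug response is the same in all three rows.

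**Simulation.** 4,000 trials per setting, n = 50, complete data. Assumed SDs: individual 0.5, individual-by-paradigm 0.3, residual 0.4. Tests are two-sided at 0.05, made by one-sample t-tests on per-person contrasts. Signs here are MID minus PFV.

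| Setting | Paradigm coefficient | Time coefficient | Paradigm × time |
|---|---|---|---|
| PFV -0.4, MID 0, equal mean levels | 0.001, rejected 4.7% | -0.201, rejected 93.2% | 0.401, rejected 93.2% |
| Both -0.2, MID level 0.5 higher | 0.500, rejected 100% | -0.200, rejected 93.0% | 0.000, rejected 4.8% |

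In the first setting only PFV responds, and the paradigm coefficient shows nothing. In the second the tasks respond identically, and it is always significant. The time coefficient is about -0.20 in both. The interaction separates the two settings.

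**With the interaction added**, the difference-in-change contrast equals the interaction coefficient exactly.

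**Missing scan 2.** Section 21.0 allows withdrawal and keeps data already collected, so some post-dose cells may be missing, and G + D/2 is then only approximate. With the SDs above, G = 0.15 and D = -0.30, generalised least squares gives bP = 0 with complete data, 0.011 (0.0105) if 10% lack scan 2, and 0.022 if 20% do.

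**Paired comparison against the interaction model.** Add an assumed session SD of 0.1 and let 20% of 50 participants have a missing cell. The complete-case paired SE is 2 × 0.4/√40 = 0.1265. The interaction model's SE, with a session term, is 0.1224 if those participants miss scan 2 entirely and 0.1187 if they lack one task's post value. The paired SE is thus about 3% and 7% larger (0.1265/0.1224 = 1.03; 0.1265/0.1187 = 1.07).

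**Session term.** With session SD s and residual SD r, leaving out an individual-by-session intercept multiplies the interaction SE by about √(1 + s²/r²): 1.05, 1.12 and 1.41 at assumed s/r of 1/3, 1/2 and 1. This costs precision and does not create a false paradigm difference.

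**The case against.** The strongest reply is that the sentence is a list of factors in a two-by-two within-person design, not a model equation. It opens with the comparison of changes, and nothing in it excludes an interaction, so the interaction is implied. This is plausible and probably what was meant. It does not settle the matter: the interaction is the one term that answers SA2, it is not written anywhere, and no coefficient is named as the test.

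A second reply is that the outcome is the change score itself, which would make the paradigm main effect correct. The text rules this out, because time (pre, post) is listed as a fixed effect and a change score already spans both times.

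A third reply is that SA1 gives each task's own change, so the difference in point estimates follows by subtraction. That stands. A reader might infer that the trial cannot answer SA2, or will certainly pick the wrong task. The documents support neither: the right contrast can be computed from the planned data, and harm arises only if the additive model is fitted and read as the SA2 result. What remains missing is a specified test and interval. Setting two t-scores side by side, the example of sensitivity in Section 2.0, does not test their difference.

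It is also fair that SA2 is secondary in a pilot study, and that different target regions do not prove a level gap within one ROI.

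**Conclusion.** The point holds as a specification gap that should be fixed. The listed terms cannot express a difference in change between PFV and MID, and this follows from the model structure without any assumed value. The form G + D/2 for the paradigm coefficient is exact with complete data; under the assumed SDs it moves by about 0.01 to 0.02 when 10 to 20% miss scan 2. The -0.15/0/+0.15 example and the simulated rejection rates rest on assumed values, and the documents do not allow the real error to be sized.

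Confidence is high that the term is not stated. It is lower that harm would follow, since an analyst may well add the interaction unprompted. The consequence is confined to a secondary aim, though that aim is meant to inform the choice of task for later work. A reader might also infer that the mixed model should give way to a paired test. That does not follow: the mixed model with the interaction answers SA2 and keeps participants with a missing cell.

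**What to change.** In Section 22.0, add the paradigm × time interaction to the SA2 fixed effects. State that its coefficient, with a 95% CI and within each a priori ROI, is the SA2 test. Report each paradigm's own pre-to-post change with its 95% CI alongside. This last item matters because the interaction measures a signed difference: assumed changes of -0.15 and +0.15 are equal in size yet give an interaction of -0.30, which should not be read as one task responding more strongly.

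Two additions are optional. The within-person paired comparison of changes can be given as a complete-case check, with a note that it drops anyone with a missing cell. An individual-by-session random intercept can be added; for the interaction it affects efficiency only.

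The cost is one or two sentences, with no change to data collection or sample size.

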3.0 Background

Naltrexone shows promise in treatment of binge eating and purging. Previous studies have demonstrated that naltrexone, a drug that interrupts the opioid reward circuit, reduces binge eating and purging in adults (1-3). Our recent retrospective case series revealed that naltrexone reduced binge/purge behaviors in approximately 60% of adolescents with no serious side effects (4). However, the patient-specific factors associated with response vs. non-response remain to be elucidated.

Naltrexone systemic exposure is highly variable. Preliminary data from our current naltrexone pharmacokinetic study demonstrate significant interindividual variability in the rate and extent to which naltrexone is absorbed in adolescents with ED. With systemic exposure varying by 16-fold, pharmacokinetic differences may contribute to variability in drug response.

Biomarkers of brain response are lacking. Opioid receptor binding studies done in adults using positron emission tomography (PET) show nearly 100% mu opioid receptor (OPRM) blockade with naltrexone 50 mg (5); however, 1 in 3 adolescents with ED fail to respond at this dose (4) and higher doses may be necessary to reach therapeutic effect in certain individuals (6, 7). Thus, biomarkers of brain response are critically needed to understand the impact of the opioid reward system, and opioid antagonism in adolescents with eating disorders.

Next Steps. Pharmacodynamic biomarkers of brain response are lacking yet are critically needed to untangle factors associated with response vs. non-response and advance precision therapeutics. This study will initiate the development of a biomarker (i.e., neuroimaging) of opioid antagonism in adolescents with eating disorders that will aid in drug development and repurposing.

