5.0 Study Design

This is an open-label, interventional trial to evaluate reward system modulation (detected by neuroimaging) in response to opioid antagonism (i.e., naltrexone) in adolescents aged 13-21 years with an eating disorder characterized by the target behaviors of binge eating and/or purging (e.g., AN-

SHORT TITLE: Naltrexone Neuroimaging

BP, BN, BED). A pre/post design completed on the same day will be employed to quantify *within-individual change* while reducing potential confounding due to known neuroimaging variables (e.g., menstrual phase, treatment changes) that may occur with time elapsed between study visits.

Up to 50 individuals may be enrolled to meet our objectives.

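### SA2's intercept-only mixed model leaves out the paradigm-by-time term and gives too wide a standard error for the paradigm comparison if a person's PFV and MID changes are positively correlated

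*Combined protocol and SAP*

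**What the plan says.** Section 22.0 (SA2, Optimal paradigm) names the method: "The %BOLD changes will be compared between paradigms by LMM". Its fixed part lists task and time as main effects, and its random part is given only as "and random individual and/or paradigm intercepts". No paradigm-by-time term is listed, and no section adds an individual-by-time effect.

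The endpoint in Section 4.0 is the "paradigm (PFV or MID) resulting in larger response", so the target is a difference between two pre/post changes.

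Section 9.0 sets the data layout: "Each participant will undergo two fMRI scans on the same day", with both tasks run in each scan. Each complete participant therefore gives four values per ROI (2 tasks x 2 times).

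On sample size, Section 5.0 says: "Up to 50 individuals may be enrolled to meet our objectives". The documents state no alpha, power, effect size, SD or variance component for any aim.

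**The concern.** There are two defects, and the second remains after the first is repaired.

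1. **Missing term.** With main effects only, the model gives an average task difference and an average pre/post difference. Neither is the difference between the two changes that SA2 asks about.

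2. **Random structure.** Random intercepts assume that everyone has the same pre/post change apart from independent noise. The protocol expects otherwise. Section 3.0 says "1 in 3 adolescents with ED fail to respond at this dose", Section 2.0 describes "widely variable maximum plasma concentrations" (17-fold), and SA3 correlates individual change with exposure. PFV and MID also share one scan session, one dose and one plasma profile. If part of a person's change is common to both tasks, these models count it as residual error, although it cancels from the SA2 contrast.

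The words 'and/or' also leave the random structure open. A literal random intercept for paradigm, with two levels shared by everyone, duplicates the fixed paradigm effect. The only useful reading is paradigm within individual.

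At stake is the power of SA2, whose purpose is to choose the task for later studies.

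**Working it through.** The plan gives no figure to reproduce. All variances below are assumptions.

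**Set-up.** Take a balanced layout with n = 50 complete participants. Let y = fixed effects (including paradigm x time) + person + person-by-paradigm (variance b) + person-by-time (variance c) + residual (variance e). The correlation between a person's PFV and MID changes is then ρ = 2c/(2c + 2e) = c/(c + e).

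**Correct standard errors.**
- Difference in change: √(4e/n). At e = 1 this is √(4/50) = 0.283. Neither b nor c enters.
- Pooled pre/post effect: √((e + 2c)/n).

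**Residual variance fitted when the person-by-time effect is omitted.**
- (A) Individual plus individual-by-paradigm intercepts: e + c.
- (B) Individual intercepts only: e + (2/3)(b + c).

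**Ratio of model SE to correct SE.** For the difference in change it is R = √(fitted residual / e). For the pooled effect it is S = √(fitted residual / (e + 2c)).

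**Power and type I error (normal approximation, two-sided 5%).** A comparison with true power of 80% has a standardised effect of 1.960 + 0.842 = 2.802. With an SE wrong by the factor R, power is Φ(2.802 − 1.960R). Type I error of the pooled test is 2[1 − Φ(1.960S)].

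Results at e = 1, b = 0.5:

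| c | ρ | Model | Fitted residual | R | SA2 power | S | Pooled type I error |
|---|---|---|---|---|---|---|---|
| 0 | 0 | A | 1.00 | 1.00 | 80% | 1.00 | 5% |
| 0.25 | 0.20 | A | 1.25 | 1.12 | 73% | 0.91 | 7.4% |
| 0.25 | 0.20 | B | 1.50 | 1.22 | 66% | 1.00 | 5% |
| 0.5 | 0.33 | A | 1.50 | 1.22 | 66% | 0.87 | 9.0% |
| 0.5 | 0.33 | B | 1.67 | 1.29 | 61% | 0.91 | 7.4% |
| 1 | 0.50 | A or B | 2.00 | 1.41 | 51% | 0.82 | 11% |

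Worked example, c = 0.5 in model B: the residual is 1 + (2/3)(1.0) = 1.67, so R = 1.29. Power is Φ(2.802 − 2.530) = Φ(0.271) = 61%.

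**General form for model A.** R = 1/√(1 − ρ) and S = 1/√(1 + ρ). At ρ = 0 both are 1. At negative ρ both directions reverse.

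**Exception for the pooled effect in model B.** S = 1 when b = 2c, because e + (2/3)(3c) = e + 2c. Above that, the pooled SE is too wide.

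**Checks.** REML fits at n = 50 with b = c = e = 1 gave mean SEs for the difference in change of 0.397 (A) and 0.429 (B), against a correct 0.283. The closed forms are 0.400 and 0.432. Adding an individual-by-time effect gave 0.281. A simulation with t critical values gave SA2 power of 62-74% at c = 0.25 to 0.5 and 53-54% at c = 1. The paired analysis gave 80% throughout.

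**The case against.** **The trigger is narrower than people differing in response.** The error needs a change component shared by both tasks. Clinical non-response and spread in Cmax do not give a cross-task BOLD correlation. Section 9.0 describes the tasks as giving distinct insight, with PFV expected to engage prefrontal regions and MID the striatum. Section 3.0 reports nearly complete receptor blockade at this dose in adults, which weakens the step from exposure spread to response spread. All of this stands: positive correlation is plausible, not documented.

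**False claims of a naltrexone effect.** A reader might infer that the plan will declare a pre/post effect too often, since the pooled time term's SE is often too narrow. The documents do not support that. SA1 response is a separate ROI analysis, and no section says the SA2 time term will be tested or reported. The type I error figures apply only if it is.

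**The error is conservative, in a pilot.** With complete data, which task looks larger does not depend on the random structure. Only the interval width and the test change. This limits the harm, but an interval wider than the data warrant still weakens the choice of task.

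**The sentence may mean that change scores are the outcome.** With one change per task and a random individual intercept, the comparison would be sound when ρ is not negative. But a pre/post time effect has no place in such a model, so the text needs correcting on either reading.

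**Conclusion.** The concern holds in limited form. As written, the SA2 model lacks the term that answers its question. With that term added, intercept-only models give too wide a standard error for the difference in change if a person's PFV and MID changes are positively correlated. With individual intercepts only, stable person-by-paradigm differences widen it further.

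Under the assumed variances, 80% power falls to about 61-73% for correlations of 0.20 to 0.33, and to about 51% at 0.50. With zero correlation and individual-by-paradigm intercepts there is no loss.

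The pooled pre/post term is secondary and matters only if it is reported as evidence of response. Its type I error would be about 5-9% at person-by-time variance 0.25 to 0.5 and about 11% at 1. With individual intercepts only, its SE is exact or too wide once person-by-paradigm variance is at least twice person-by-time variance.

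The directions follow from algebra. The sizes rest on variances that the documents do not give. The change is worth making because the paired analysis is valid whatever the correlation.

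**What to change.** In Section 22.0, SA2, replace the model sentence with one of these:

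- **Paired analysis.** For each ROI, compute per participant D = (PFV post − PFV pre) − (MID post − MID pre). Report the mean of D with a paired t-based 95% CI.
- **Mixed model.** Use paradigm, time and paradigm x time as fixed effects, with an unstructured 4x4 within-person covariance. This also uses participants with incomplete pairs.

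Delete 'and/or' and the random paradigm intercept.

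A model with individual, individual-by-paradigm and individual-by-time effects should not be called equivalent in general. It matches the paired analysis only when no variance estimate is truncated at zero, and it cannot represent a negative cross-task correlation.

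The cost is a sentence or two of analysis text, with no new data or procedures. The paired version drops participants who lack any of the four values, and the mixed model avoids that.
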